6.0 Study Device

6.1 General Description

The Pure-Vu System is Food and Drug Administration (FDA) cleared device, intended to connect to standard colonoscopes to help facilitate intra-procedural cleaning of a poorly prepared colon by irrigating or cleaning the colon and evacuating the irrigation fluid (water), feces and other bodily fluids and matter, e.g. blood.

The Pure-Vu System comprises the following components:

- The Pure-Vu Workstation (WS) - controls the flow of gas (e.g. air) and water or saline to the Oversleeve device and the evacuation of fecal matter and fluids out of the body.
- The disposable Oversleeve is mounted on top of the colonoscope allowing the physician to clean the colon. The Oversleeve is connected to WS via the WS Connector (WSC).
- The disposable WS Connector is mounted onto the front panel of the WS and connects to the irrigation and sensing lines of the Oversleeve.

Document Title: Evaluation of the bowel cleansing in hospitalized population using Pure-Vu System	Document No. CL00044	Version 4.0	Page 13 of 44
---	--------------------------------	-----------------------	---------------

- The loading fixture is an ancillary device that is used to aid in loading the device on the colonoscope.
- External reservoir for collecting the evacuated fecal matter and fluids
- External foot pedals that operate the cleansing and evacuation process to be used by the investigator.

Below is a drawing showing the various components of the system and where they connect to each other.

[figure not shown]

Figure 1: Pure-Vu Workstation – General design & components

A detailed description of the system components, its principles of operation, dimensions and packaging is elaborated in the Instruction for use (IFU).

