9.0 Study Endpoints

9.1 Primary endpoints

The rate of improved cleansing level per segment will be evaluated by the BBPS (1) scoring index pre- and post- Pure-Vu use during a colonoscopy examination.

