11.1 Inclusion Criteria

1. Hospitalized subjects who are indicated for a screening, diagnostic, surveillance or therapeutic colonoscopy
2. Subjects' age > 22 years
3. Subject has signed the informed consent

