12.4 Colon Preparation

As standard practice in the hospitalized population setting, bowel preparation is prescribed for individuals undergoing a colonoscopy procedure. The typical and recommended bowel prep is the 4 Liters of GoLytly as a split dose. Although this bowel prep is widely prescribed, it is not a requirement that the subject completes the bowel prep prior to the colonoscopy procedure for the study.

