12.5 Colonoscopy procedure

Pre-Examination Procedures

- Verify eligibility checked and informed consent was obtained after explaining all risks, benefits, and alternatives to the subject.
- Verify that the study coordinator/nurse has completed the questionnaire regarding the subject's bowel cleansing condition.
- Verify all background/clinical information, demographic and medical history was documented

Document Title: Evaluation of the bowel cleansing in hospitalized population using Pure-Vu System	Document No. CL00044	Version 4.0	Page 26 of 44
---	--------------------------------	-----------------------	---------------

- Verify all connections and assemblies are properly attached (see Instructions for Use)
- Verify device works properly (see Instructions for Use)
- Place and prepare the subject for the colonoscopy procedure.

Colonoscopy Procedures

The insertion during the colonoscopy procedure will be performed by the clinical study investigator(s), experienced in GI endoscopy according to local standard of care. The withdrawal part of the colonoscopy procedure will be performed as per the clinical investigator(s) direction. Physicians in training (residents, fellows) and physician assistants may assist the Study Investigator in any aspect of this part of the procedure as per standard procedures and practices at his/her institution. In cases where upper endoscopy is planned, it will be conducted per the physician's discretion. Anesthesia will be applied as well per the standard of care. In order to ensure correct operation of the Pure-Vu System a Motus GI representative may attend the procedure. Pure-Vu System operation is described in the Instruction for Use.

The colon preparation level for each colorectal segment (ascending, transverse and descending) before the cleansing operation during the insertion phase will be evaluated using the BBPS scoring index (Appendix B).

In case of inadequate bowel preparation defined as BBPS less than 2 in at least one of the colon segments prior Pure-Vu use, the physician will complete a questionnaire as it relates to the subjects management standard of care assuming absence of the Pure-Vu System.

Once the procedure is completed, relevant data will be recorded on the CRF in addition, findings, diagnosis as well as Physician questionnaire will be recorded/completed.

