13.3 Primary Endpoint Analysis

The primary endpoint is improving the bowel cleansing level, as determined by BBPS scoring index, assessed per segment (cecum and ascending / transverse / descending, sigmoid and rectum).

The primary statistical hypothesis is that the cleansing level post Pure-Vu procedure will be significantly improved as compared to the cleansing level pre procedure (prior the Pure-Vu use). The primary performance assessment will be based on data from all colon segments observed during the colonoscopy procedure.

The count and percentage of segments and subjects with improved BBPS after the Pure-Vu cleansing procedure will be presented together with 95% confidence intervals.

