20.0 Appendixes A: Study Design and Schedule of Assessment

	Visit 1	Follow Up
Days	0	2 Business Days (± 48 hours)
Informed Consent	X	
Eligibility assessment (medical records, BMI, etc.)	X	
Medical History, Concomitant Medications, and Demographic details	X	
Assessment of patient's bowel preparation questionnaire	X	
*Assessment of patient's management Directions (filled-in by the physician)	X	
Colonoscopy Procedure	X	
Follow Up	X	X
Adverse Events Reporting	X	X

*for subjects with inadequate bowel cleansing level in at least one segment at baseline.

Document Title:	Document No.	Version	Page 44 of 44
Evaluation of the bowel cleansing in hospitalized population using Pure-Vu System			

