21.0 Appendix B: Boston Bowel Preparation Scale

- ❖ **A:** Score 0- Unprepared colon segment with mucosa not seen due to solid stool that cannot be cleared.
- ❖ **B:** Score 1 - A portion of the mucosa of the colon segment is seen, but other areas of the colon segment are not seen well due to staining, residual stool, and/or opaque liquid.
- ❖ **C:** Score 2- A minor amount of residual staining, small fragments of stool, and/or opaque liquid are visible, but the mucosa of the colon segment are seen well.
- ❖ **D:** Score 3- The entire mucosa of the colon segment is seen well with no residual staining, small fragments of stool, or opaque liquid.

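### The 13.3 improvement rate includes segments already at the BBPS maximum, so alone it cannot show how often the device cleans segments that need cleaning

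*Combined protocol and SAP*

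**What the plan says.** Section 9.1 defines the primary endpoint: "The rate of improved cleansing level per segment will be evaluated by the BBPS (1) scoring index pre- and post- Pure-Vu use". Section 13.3 adds: "The primary performance assessment will be based on data from all colon segments observed during the colonoscopy procedure". It then plans the number and proportion improved, by segment and by subject, with 95% confidence intervals. It does not say what size of change counts as improved, and it names no test for the pre/post hypothesis.

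Entry is open as to preparation. Section 11.1 admits "Hospitalized subjects who are indicated for a screening, diagnostic, surveillance or therapeutic colonoscopy", and none of the twelve exclusions in 11.2 concerns cleanliness of the colon. On the bowel preparation, section 12.4 says "it is not a requirement that the subject completes the bowel prep prior to the colonoscopy procedure for the study".

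A baseline cut-off does appear, but only to trigger a physician's questionnaire. Section 12.5 words the condition as "In case of inadequate bowel preparation defined as BBPS less than 2 in at least one of the colon segments prior Pure-Vu use". The footnote in Appendix A limits that form to one group, "for subjects with inadequate bowel cleansing level in at least one segment at baseline", so adequately prepared subjects are expected as well.

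In Appendix B the top score, 3, means: "The entire mucosa of the colon segment is seen well with no residual staining". Section 13.5 removes withdrawals, technical failures and failures to reach the intended segment from the primary analysis. It removes nothing on the basis of baseline score.

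**The concern.** Section 6.1 gives the device's purpose as to "help facilitate intra-procedural cleaning of a poorly prepared colon". The primary percentage is taken over a wider set that includes segments with nothing left to clean. A clean segment that stays clean and a dirty segment that stays dirty add the same amount to the denominator and nothing to the numerator.

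What is at stake is how the headline figure can be read. A low rate could mean that the device often failed, or that many segments were already clean. Rates from the up to six sites could differ through preparation practice alone. The plan specifies no pre-by-post tabulation and no breakdown by baseline score that would separate these explanations.

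**Working it through.** The plan states no target rate and no sample-size basis (13.1), so there is no design figure to reproduce. The check is how far the reported rate can move when device performance is fixed.

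**Inputs from the documents.** Up to 100 subjects (10.0, 13.1) with three segments each gives up to 300 segments. Scores run from 0 to 3 (Appendix B). In the earlier clinical data, obtained under deliberately reduced preparation, the mean baseline total was 3.9, and 25% of subjects had all three segments at 2 or more (6.3).

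**Assumed inputs.** *f* is the share of segments at baseline 3, and *q* is the improvement rate among segments at baseline 0 to 2. Neither is given. Any one-point rise is taken as improvement.

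**Formula.** A segment at 3 cannot rise, so the all-segment rate is (1 − f) × q. With q = 100% the rate cannot exceed 1 − f.

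| f (assumed) | Cap, 1 − f | Rate if q = 95% | Rate if q = 90% |
|---|---|---|---|
| 5% | 95% | 90.3% | 85.5% |
| 10% | 90% | 85.5% | 81% |
| 20% | 80% | 76% | 72% |
| 30% | 70% | 66.5% | 63% |
| 40% | 60% | 57% | 54% |

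**The same result from different devices.** Suppose 189 of 300 segments improve, a rate of 63%. That fits f = 0 with q = 63%, f = 10% with q = 70% (0.90 × 0.70 = 0.63), or f = 30% with q = 90% (0.70 × 0.90 = 0.63). The all-segment figure cannot tell these apart. A pre/post table can.

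**What the earlier data say about f.** The mean per segment was 3.9 / 3 = 1.3. Whatever the distribution, the share at 3 cannot exceed 1.3 / 3 = 43%, so the cap in that population was at least 57%. For a point illustration, take scores as binomial(3, p) with p = mean total / 9:

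- Mean 3.9: p = 0.433, f = 0.433³ = 0.081, cap about 92%.
- Assumed mean 6: p = 0.667, f = 0.667³ = 0.296, cap about 70%.

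This model is rough. At p = 0.433 the chance that a segment scores 2 or more is 3p²(1 − p) + p³ = 0.401. With independent segments, about 0.401³ = 6% of subjects would then have all three at 2 or more, against the 25% reported. The binomial figures show only that the cap can move a long way.

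**Subject level.** If one improved segment is enough, only subjects at 3 in every segment are capped. At the assumed mean of 6 with independent segments that is 0.296³ = 2.6%, and more with clustering. The effect is mainly on the segment rate.

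**If improvement meant crossing from below 2 to 2 or more.** Segments at baseline 2 could not improve either, and the cap would fall to 1 minus the share at 2 or more. Leaving the term undefined therefore does not remove the problem.

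**The case against.** The strongest reply is that the all-segment rate is a legitimate target. The objective in 8.1 and the design in 10.0 concern hospitalized subjects in general, and how often use in such patients raises the score properly depends on how they arrive. This stands. A reader might infer that the planned rate is invalid or should be replaced as primary; the documents do not support that. Replacement is also debatable on its own terms: improvement is undefined, and selecting segments on a low baseline score, with no blinded or independent scoring described in 12.5, invites regression to the mean.

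A reader might also infer that the plan labels baseline-3 segments as failures. It does not say so, and it names no denominator for the percentage. The sentence on observed segments could be read as a rule about segments that were not reached. The all-segment reading is the natural one, but it is a reading.

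Nor is bias in the primary inference shown. No target rate depends on the figure, and the cap can only lower it. Under a sign or McNemar-type paired test, segments at 3 before and after would be ties and carry no weight.

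Lack of comparability with the earlier studies is another tempting inference. Section 6.3 reports subject adequacy and mean scores, not a rate of improved segments, so there is no earlier figure of this kind to compare.

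Two further replies stand only in part. Section 5.1 names inpatient status as a risk factor for poor preparation, so f may be modest; but even under reduced preparation 25% of subjects were adequate in all segments, and nothing supports taking f as zero. Section 13.2 allows post-hoc analysis, but a denominator chosen after the results are seen is less convincing than one fixed beforehand.

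**Conclusion.** The point holds as a matter of interpretability. On the natural reading of 13.3, the segment improvement rate is capped at 1 minus the share of segments at baseline 3: 95% to 60% if that share is 5% to 40%. For an unchanged device that improves 95% of the segments able to improve, the reported rate would run from about 90% to 57% over the same range. These sizes rest on an assumed share and on any one-point rise counting as improvement.

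The rate remains a valid description of use in unselected inpatients in a pilot with no decision threshold. What it cannot do alone is show how often the device cleans segments that need cleaning.

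**What to change.** In 13.3:

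1. Define improvement, for example as any rise in segment BBPS.
2. Keep the all-segment rate as planned.
3. Prespecify beside it the rate, with 95% confidence interval, among segments with baseline BBPS 0 to 2, and the matching rate among subjects with at least one such segment.
4. Report the share of segments with baseline below 2 that reach 2 or more, which matches the adequacy threshold used elsewhere in the protocol.
5. Add a 4x4 table of pre against post BBPS, with baseline-3 segments shown as maintained or worsened.

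This is a change of wording plus tabulation of scores already collected; enrollment and procedures are unaffected. Two costs should be acknowledged. Intervals widen: at a rate of 90%, treating segments as independent for illustration only, the approximate half-width is 1.96 × √(0.9 × 0.1 / 300) = 3.4 points with 300 segments and 1.96 × √(0.9 × 0.1 / 210) = 4.1 points with 210 (f = 30%). Restricting on a low baseline score may also push the restricted rates upward through regression to the mean, which should be stated where they are reported.

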13.4 Secondary Endpoints Analysis

13.4.1 Safety Analysis

The secondary endpoint is to evaluate the device related adverse event and the overall adverse events rate. The safety analysis set will consist of all subjects who were enrolled into the study.

Document Title: Evaluation of the bowel cleansing in hospitalized population using Pure-Vu System	Document No. CL00044	Version 4.0	Page 29 of 44
---	--------------------------------	-----------------------	---------------

Individual listings of adverse events including type, reported term, seriousness, duration, relationship to the study device, severity and the adverse events outcome will be provided for the total population. AEs will be summarized using frequency counts and percentages.

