11.0 Subject Selection and Enrollment

After being informed of the study, the subject will sign the sites' designated IRB approved informed consent form (ICF). Enrollment of up to 100 subjects is planned.

Subjects' participation in the study will last approximately 3 days, including the procedure day, and the follow up period.

Subjects will be considered for the study if they meet the specific inclusion/exclusion criteria. The criteria for enrollment must be followed explicitly.

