12.3 Screen Failures

A subject is considered enrolled in the study when the ICF is signed. Only subjects who undergo the colonoscopy procedure with Pure Vu will be followed. Subjects who provide study consent, but then are determined to be ineligible will be considered screening failures and will not require additional study follow-up. The reason for the screening failure will be clearly documented, the Subject "Enrollment and Visit Log" will be completed and the subject eligibility section in visit 1 as well as a "Study Completion" form will be completed in the CRF.

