13.5 Analysis Populations

Cases withdrawn prior to the Pure-Vu procedure and those with technical failures will be excluded from the primary analysis. Cases with failure to reach the desired colon segment per the intended indication, which cannot be conducted with Pure-Vu, will be excluded from the primary analysis. All subjects who have the Pure-Vu inserted will be included in the safety analysis.

Individual listings of withdrawal / technical failure including descriptive information will be provided.

Document Title:	Document No.	Version	Page 30 of 44
Evaluation of the bowel cleansing in hospitalized population using Pure-Vu System	CL00044	4.0	

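### Section 13.4.1 builds the safety set from all consented subjects while 13.5 refers to Pure-Vu insertion, so never-exposed subjects can dilute the device-related AE rate

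*Combined protocol and SAP*

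**What the plan says.** Section 13.4.1 names two safety rates, device-related AEs and AEs overall, and sets their population: "The safety analysis set will consist of all subjects who were enrolled into the study". The method of summary is "AEs will be summarized using frequency counts and percentages", so the safety set is the denominator.

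The only stated definition of enrollment is in Section 12.3: "A subject is considered enrolled in the study when the ICF is signed". The same section adds "Only subjects who undergo the colonoscopy procedure with Pure Vu will be followed", and says of those found ineligible after consent: "Subjects who provide study consent, but then are determined to be ineligible will be considered screening failures and will not require additional study follow-up".

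Section 13.5, which deals with analysis populations, says "All subjects who have the Pure-Vu inserted will be included in the safety analysis". It also foresees subjects lost before exposure, but removes them from one analysis only: "Cases withdrawn prior to the Pure-Vu procedure and those with technical failures will be excluded from the primary analysis".

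Section 11.0 sets the size: "Enrollment of up to 100 subjects is planned". Section 14.1 starts AE collection at enrollment. Section 8.2 makes device safety a secondary objective.

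**The concern.** Taken together, 13.4.1 and 12.3 put every consented subject into the AE denominator, including screening failures and those withdrawn before the procedure. Section 13.5 points to an exposed population. Two analysts could each follow the plan and report different percentages.

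The two denominators do not err symmetrically. A subject in whom the device was never used cannot contribute a device-related event but still adds one to the denominator. Any error from using all consented subjects therefore makes the device look safer. Because 12.3 does not follow these subjects, their other AEs are also less likely to be recorded.

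What is at stake is the headline device-related AE rate in a single-arm pilot. No safety threshold, test or stopping rule uses it.

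**Working it through.** **Which subjects differ between the two sets.** They are those with a signed consent form and no Pure-Vu insertion. The plan expects some: screening failures after consent (12.1 and 12.3) and withdrawals before the procedure (13.5). Neither section takes them out of the safety set defined in 13.4.1.

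**Whether other sections settle the matter.** They do not, because enrollment is used in two senses. The synopsis sets the interim analysis at 45 enrolled subjects, while Section 13.6 counts 45 completed procedures. So 13.4.1 may have meant treated subjects, but the only written definition is consent.

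**Inputs.** The cap of 100 comes from Section 11.0. The plan states no AE rate and no unexposed share, so there is no figure of its own to reproduce. Assumptions: f, the share of consented subjects never exposed, from 0 to 30%; and 4 subjects with a device-related AE, for illustration.

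**Device-related AEs.** Let N be the number consented and p the rate in exposed subjects. Affected subjects number p(1 − f)N. Dividing by N gives

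reported rate = p(1 − f).

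The relative understatement equals f, whatever p is.

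With N = 100, the all-consented denominator gives 4/100 = 4.0%, exact (Clopper-Pearson) 95% CI 1.1% to 9.9%. The zero-event column is the two-sided 95% upper limit, 1 − 0.025^(1/n).

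| f | Exposed n = 100(1 − f) | Multiplier 1 − f | 4/n (exact 95% CI) | Upper limit, 0 events |
|---|---|---|---|---|
| 0 | 100 | 1.00 | 4.0% (1.1–9.9) | 3.6% |
| 5% | 95 | 0.95 | 4.2% (1.2–10.4) | 3.8% |
| 10% | 90 | 0.90 | 4.4% (1.2–11.0) | 4.0% |
| 20% | 80 | 0.80 | 5.0% (1.4–12.3) | 4.5% |
| 30% | 70 | 0.70 | 5.7% (1.6–14.0) | 5.1% |

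The choice of 4 events does not drive the ratio. With 5 events the rate is 5.0% on 100 and 5/80 = 6.25% on 80, again a multiplier of 0.80.

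**Overall AEs.** Let r be the recorded AE rate in unexposed subjects relative to exposed subjects. Then

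reported rate = p(1 − f) + r·p·f = p[1 − f(1 − r)].

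At an assumed r = 0.5 the multiplier is 1 − 0.05 × 0.5 = 0.975 at f = 5% and 1 − 0.30 × 0.5 = 0.85 at f = 30%. At r = 1 there is no dilution, and above 1 the direction reverses.

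**The case against.** The strongest reply is that the two sections do not conflict. Section 13.5 does not limit the safety analysis to inserted subjects. Its sentence follows two exclusions from the primary analysis and may simply mean that those exclusions do not carry over to safety. That reading is fair, and the sentences are logically compatible. But it leaves 13.4.1 in charge of the denominator, and so leaves the dilution in place.

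A second reply is that an all-enrolled set suits the overall AE rate, since AEs are collected from enrollment. This stands in part. The direction for overall AEs is not established: withdrawal for newly appearing illness (11.3) could raise r above 1, while the absence of follow-up pulls it down. The firm claim concerns device-related AEs only.

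Third, the size is assumed. Nothing in the documents supports a share as high as 20% or 30%, and Appendix A places consent and colonoscopy in the same visit on Day 0, which favours the low end. This stands too.

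Finally, individual listings of AEs, withdrawals and technical failures are planned, and screening failures are logged, so a reader with access to these could rebuild an exposed denominator. That limits the harm but does not correct the reported percentage.

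**Conclusion.** The point holds. As written, the plan admits never-exposed and unfollowed subjects to the denominator of the device-related AE rate, and no section says that an exposed population should be used instead. The reported rate is 1 − f times the rate in exposed subjects: 0.95 at f = 5%, 0.70 at f = 30%, and unchanged if f = 0.

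At the likelier low end the shift is small (4.0% against 4.2% in the illustration), and the confidence intervals overlap heavily throughout. The result would be a misstated descriptive rate, not a wrong formal decision. It should still be corrected, because the error can only favour the device on a named secondary endpoint and a wording change removes it. The size rests on the assumed f and event counts; the direction for device-related AEs does not.

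**What to change.** In Section 13.4.1, define the safety set for AE rates as all subjects in whom insertion of Pure-Vu was attempted or made, and use identical wording in 13.5. Counting attempts keeps a failed insertion from dropping out of the safety data.

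State that a subject already exposed stays in the set even if later found ineligible. This can happen: the third exclusion criterion in 11.2 includes obstruction found during the colonoscopy itself, and 12.1 withdraws ineligible subjects without further follow-up.

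List AEs in other consented subjects separately, so that events collected from consent onward are not lost. Report the numbers consented, attempted and inserted, so that a reader can recompute any rate.

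The cost is wording in two sections and one line of subject counts, with no new data. Device-related AE percentages may read slightly higher.
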